Study Title: Dornase Alfa for ARDS in Patients
with SARS-CoV-2

NCT number: 04402970

Document Date: Last approved/updated
3/08/2021

Background and Significance

Health care systems across the world are being inundated with patients who are critically ill due to infection with Severe Acute Respiratory Syndrome-Coronavirus-2 (SARS-CoV-2) causing Coronavirus Disease 2019 (COVID-19). Around 10% of those infected will develop the most severe manifestation of the disease requiring admission to an intensive care unit¹. Early reports suggested neutrophil extracellular traps (NETs) as being a potential contributor to the severity of disease in some patients with COVID-19². The primary innate immune role for NETs is to trap and kill invading microbes, but in severe cases of COVID-19, NETs appear to cause significant morbidity in the lungs with associated microthrombi formation, endothelial damage, capillaritis, neutrophilic mucositis and mucus accumulation³⁻⁶. Plasma levels of NET activity are increased in patients who requiring intubation and are inversely correlated with arterial blood oxygen content to fraction of inspired oxygen ratio ($\text{PaO}_2/\text{FiO}_2$)⁷. Dornase alfa, currently is in use in patients with Cystic Fibrosis, works by degrading large extracellular DNA in the airways^{8,9}. We proposed a trial of using inhaled dornase alfa as a therapeutic target to reduce excess NETs in patients with acute respiratory distress syndrome (ARDS) secondary to COVID-19 pneumonia, with outcome aims including improved lung compliance and gas exchange¹⁰.

Aims and Objectives

Aim #1: Determine if use of nebulized dornase alfa in ARDS secondary to COVID-19 will lead to improved pulmonary mechanics as measured by surrogate values of $\text{PaO}_2/\text{FiO}_2$ and static lung compliance.

Aim #2: Determine if use of nebulized dornase alfa in ARDS secondary to COVID-19 will lead to a reduction in alveolar and serum NET activity.

Research Design

A single center, non-randomized, controlled before-and-after clinical study was designed to examine the effects of inhaled dornase alfa in patients with acute respiratory distress syndrome secondary to COVID-19 pneumonia. A second standard of care patient population is to be collected as a case control group for comparison. After inclusion to the study and consent has been obtained, we will collect blood samples and perform diagnostic flexible bronchoscopy with bronchoalveolar lavage (BAL). Patients will then receive nebulized dornase alfa via vibrating mesh nebulizer through the ventilator circuit twice daily for 3 days. On day 4 after randomization, blood samples and BAL fluid samples will again be collected to determine change in serum and alveolar NET activity. Therapy will be discontinued in any patients who develop treatment failure defined as an increase in FiO₂ by 20%, reduction in static lung compliance by more than 10 or need for rescue therapies such as extracorporeal membrane oxygenation (ECMO) or inhaled nitric oxide. Primary outcome measure will be change in arterial oxygen saturation to inhaled fraction of oxygen (PaO₂/FiO₂) before and after therapy. Secondary outcomes to be included will be change in static lung compliance, duration of mechanical ventilation, length of ICU stay, length of hospitalization, secondary bacterial infections, and mortality.

Study Population and Data Collection

Patients are to be recruited from the medical intensive care unit at the University of Missouri, a 250-bed academic tertiary care medical center, after confirmation of ARDS secondary to SARS-CoV-2 infection and progression of care to requiring mechanical ventilation. Inclusion criteria included age \geq 18 years, hospitalized, and mechanically ventilated for illness related to SARS-CoV-2 infection, with individual or surrogate ability to sign informed consent, and negative urine-based pregnancy test in female patients. Exclusion criteria included contraindication or intolerance to dornase alfa, length of mechanical ventilation expected to be less than 48 hours, life expectancy less than 24 hours based upon judgment of treatment physician, pregnancy, or inability to obtain informed consent. For the first

5 days and at day 14 if applicable, daily measurements of PaO₂/FiO₂, static lung compliance, and positive end expiratory pressure (PEEP) will be collected. Demographic and clinical data of the patients to be obtained from electronic medical records at enrollment. Clinical study information will include age, sex, co-morbidities, therapies received, serological testing, ventilator data, bacterial and viral culture data, days of hospitalization, days in the intensive care unit, days of mechanical ventilation and mortality.

Primary Statistical Plan and Analysis

The primary hypothesis for this study is that by giving an inhaled medication targeting alveolar NET formation there will be an improvement in alveolar gas exchange. A control group for comparison is added who will have received standard of care. Improvement in alveolar gas exchange will be defined as a change in PF ratio from baseline for both the treatment and control groups with comparison of 95% CI between groups. Secondary endpoints of change in static lung compliance and change in PEEP will be analyzed in a similar fashion to change in PF ratio. The study is not powered to determine additional secondary endpoints such as mortality and length of hospitalization, but values will be collected and analyzed as unpaired t-test with significant p-value < 0.05. Bronchoalveolar fluid analysis for MPO-DNA will be compared before and after therapy with paired t-test analysis with significant p-value < 0.05.

Potential Impact

Resources

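### Ventilator, ICU and hospital days have no stated time origin and controls have no index day, so treated stays can look longer with no drug effect

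*Combined protocol and SAP*

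**What the plan says.** Research Design describes "A single center, non-randomized, controlled before-and-after clinical study" with a separately collected standard-of-care comparison group. Its secondary outcomes include "duration of mechanical ventilation, length of ICU stay, length of hospitalization". Study Population and Data Collection lists the matching variables only by name: "days of hospitalization, days in the intensive care unit, days of mechanical ventilation and mortality". Neither section says whether a count starts at admission, intubation, enrolment or first dose.

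Patients are recruited "after confirmation of ARDS secondary to SARS-CoV-2 infection and progression of care to requiring mechanical ventilation". Research Design then places consent, blood sampling and a lavage bronchoscopy before the first nebulized dose. No maximum is set on prior ventilator, ICU or hospital days. Two exclusions bear on length of stay: "length of mechanical ventilation expected to be less than 48 hours, life expectancy less than 24 hours". The text does not say whether they also apply to controls, and it gives controls no index day or matching rule.

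Primary Statistical Plan and Analysis assigns an unpaired t-test at the 0.05 level to the additional secondary endpoints. It names length of hospitalization as an example and says the study is not powered for them.

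**The concern.** Every treated patient has spent some time in hospital and on the ventilator before the drug can act. To be dosed at all, the patient must have stayed alive and ventilated through consent and lavage. If the durations run from admission or intubation, that waiting time is part of the treated total, and patients extubated early can never enter the treated group. A control picked from the same unit without a comparable condition can be someone who came off the ventilator early. The two groups then differ in expected duration before any drug effect.

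The comparison is tested at 0.05. A difference produced by selection could be reported as prolonged ventilation or stay, or could hide a real shortening. This is separate from how deaths are handled in a length-of-stay comparison, because it arises even if nobody dies.

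**Working it through.** The documents give no mean, SD, sample size or entry delay for any of these outcomes, so there is no planned figure to reproduce. Every duration, delay and group size below is an assumption used to test the mechanism. The only input from the plan is the unpaired t-test at 0.05, taken as two-sided because sidedness is not stated.

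**Closed form.** Let T be total ventilator days with mean 12 and no drug effect. Treated patients must satisfy T > d, where d is the entry day. Controls are unconditioned and counted from intubation.

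- Constant extubation rate (exponential): E[T | T > d] = d + 12. For d = 1, 3, 5 this gives 13, 15, 17 days against 12, an excess of 1, 3, 5 days. Time remaining after entry has mean 12, as in controls.
- Extubation rate rising with time (gamma, shape 2, scale 6, mean 2 × 6 = 12): mean remaining time is 6(12 + d)/(6 + d).
  - d = 1: 6 × 13/7 = 11.1, total 12.1.
  - d = 3: 6 × 15/9 = 10.0, total 13.0.
  - d = 5: 6 × 17/11 = 9.3, total 14.3.

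The excess is then about 0.1, 1.0 and 2.3 days, well below the exponential case.

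**Simulation with a varying delay.** Ventilator days were gamma with mean 14 and shape 1 or 2. The delay from intubation to enrolment was uniform from 0 to twice its mean. Treated patients had to be ventilated at enrolment with more than 2 days to go. Controls had to be ventilated more than 2 days in total, with no delay condition. There was no drug effect, and days were counted from intubation in both groups.

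| Mean delay (days) | Treated minus control, shape 1 | Treated minus control, shape 2 | Rejection rate, 30 per group, shape 1 | Rejection rate, 30 per group, shape 2 |
|---|---|---|---|---|
| 1 | +1.0 | +0.5 | 0.063 | 0.050 |
| 2 | +1.9 | +1.0 | 0.083 | 0.066 |
| 4 | +3.5 | +2.2 | 0.167 | 0.139 |
| 7 | +5.8 | +3.9 | 0.361 | 0.349 |

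The shape 1 difference falls short of the nominal delay because patients with long delays are less likely to qualify. At a nominal 4 days, the realised mean delay is 19.56 − 15.94 = 3.62.

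**What removes the bias.** The same simulation was run under three other control or counting rules.

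- Controls meet the same delay condition: the difference is within 0.12 days of zero (simulation error) and the rejection rate is 0.036 to 0.054. This holds whether days are counted from intubation or from the index day.
- The clock is restarted in treated patients only, with controls still counted from intubation: about 0 with shape 1, but −0.5 to −1.9 days with shape 2 for mean delays of 1 to 7 days. A one-sided correction can reverse the bias.
- The more-than-2-days condition applies to treated patients only, with zero delay: this alone adds 14.48 − 13.99 = 0.5 days (shape 2) to 15.92 − 13.97 = 2.0 days (shape 1).

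Only ventilator days were modelled. The selection argument carries over in kind to ICU and hospital days, but no size was computed for them.

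**The case against.** **Time origin.** A reader might infer that the plan collects whole-stay totals, so that pre-dose days are certainly included. The documents do not say so. They only name the variables, and elsewhere they use a study-day clock: repeat sampling on day 4, daily measurements for five days and again at day 14. Counting from enrolment is compatible with the text. What stands is that the origin is undefined and that the plain meaning of the variable names permits the whole-stay count.

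**Cause.** A reader might also infer that the start of the count creates the bias by itself. It does not. When controls meet the same still-ventilated condition, whole-stay counts show no null difference. The bias needs controls who were not selected at a comparable point.

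**Controls.** The entry criteria are not expressly limited to treated patients, and change in PF ratio from baseline is required in both groups, so controls must have some baseline day. That is a fair point, but no rule places that day at a comparable time in the course of ventilation. The implied baseline therefore does not settle the matter.

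**Variance.** It is tempting to add that pre-dose days inflate the variance of both groups. In the closed-form model with a fixed entry day, the total is d plus the remaining time. That shifts the mean and adds no variance. The point is not claimed here.

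**Importance.** The endpoints are secondary and declared unpowered, and neither aim depends on them. This limits the weight of the point. It does not remove it, because low power does not correct bias and the plan still applies a significance test.

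**Conclusion.** The concern holds in a limited form. Three things are missing together: a time origin for the durations, a cap on (or at least a record of) prior days by group, and a control index day. With all three open, the plan can be followed as written and still yield a biased comparison.

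The size cannot be taken from the documents. Under the assumptions shown, the null excess in ventilator days runs from near zero to about 6 days. With 30 per group, the false-positive rate is close to nominal at a mean delay of 1 day and about 0.35 at 7 days. The documents do not support saying that treated stays will be lengthened. The excess is zero if controls meet the same condition at a comparable day, and controls indexed later than treated patients would reverse its sign.

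PaO₂/FiO₂, static compliance and the NET measurements are not affected.

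**What to change.** Define one day 0 in both groups. In treated patients it is the day of first dose. In controls it is a matching day of ventilation on which the control is alive, ventilated and meets the same eligibility criteria. State the matching rule. Count ventilator, ICU and hospital days from day 0 in both groups, not in the treated group alone. Record ventilator, ICU and hospital days before day 0 and report them by group as baseline variables. Whole-stay totals can remain as description, without a test.

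The change needs no new patient procedures, because the dates should be available in the electronic records already used for data collection. It is more than a wording change: someone must assign index days to controls, and some candidate controls may become ineligible.

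### The primary PF-ratio comparison with a non-randomised control group has no control-selection rule, no Day 0 for controls and no named PF day, so timing, case mix or regression to the mean can mimic or hide a drug effect

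*Combined protocol and SAP*

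**What the plan says.** Research Design describes "A single center, non-randomized, controlled before-and-after clinical study" and adds the comparator in one sentence: "A second standard of care patient population is to be collected as a case control group for comparison". The analysis section says only that this group will have had standard of care.

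Primary Statistical Plan and Analysis sets the outcome for the comparison: "Improvement in alveolar gas exchange will be defined as a change in PF ratio from baseline for both the treatment and control groups". The method it gives for judging the two groups against each other is no more than this: "with comparison of 95% CI between groups". Compliance and PEEP are to be analysed in a similar way.

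On timing:
- Research Design defines the primary outcome as PF change from before therapy to after it. Dornase alfa is given "through the ventilator circuit twice daily for 3 days".
- Study Population and Data Collection has PF measured daily for the first 5 days and at day 14 if applicable. It adds: "Demographic and clinical data of the patients to be obtained from electronic medical records at enrollment".
- Day 4 appears once, for other samples: "On day 4 after randomization, blood samples and BAL fluid samples will again be collected".

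On eligibility, two exclusions are forward-looking judgements: "length of mechanical ventilation expected to be less than 48 hours, life expectancy less than 24 hours based upon judgment of treatment physician". The plan does not say whether or how they apply to controls.

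**The concern.** In a non-randomised comparison, the rule that picks the controls and the day on which their clock starts take the place of randomisation. Here neither is written down. A treated patient's clock can be inferred from the first dose. A control has no therapy, so a definition by before and after therapy gives that patient no baseline and no follow-up day.

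Two analysts following the text could choose different controls, control baselines and PF days, and report different primary results. A reader could not check any of these choices against the plan. Change from baseline removes stable differences in level between the groups. It does not remove regression to the mean, differences in when patients are caught in their illness, or case mix. An inert drug could look effective, or a real effect could be hidden.

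**Working it through.** **No figure to reproduce.** The documents give no sample size, SD, effect size or power for the primary comparison. The omissions are established by reading; the sizes below are illustrations.

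**What the text fixes for each group**

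| Item | Treated | Control |
|---|---|---|
| Source | ventilated COVID-19 ARDS, one ICU, listed criteria | standard-of-care population; period, sampling and criteria not stated |
| Day 0 | inferable from first dose | not stated |
| PF day | after a 3-day course: about day 3, 4 or 5, or day 14 | not stated |
| Adjustment | change score only | change score only |

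**Assumed inputs (none in the documents):** SD of PF 50 mmHg, baseline-to-follow-up correlation r = 0.3–0.7, n = 20–30 per group, two-sided 5% tests, inert drug unless stated. Rates are from simulation, 20,000 runs per setting.

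**1. Timing.** Suppose PF falls 5 mmHg/day for the first 3 ventilated days and is then flat, and the treated clock starts 2 days later than the control clock.
- Control, days 0 to 4: 0 to −15, change −15. Treated, days 2 to 6: −10 to −15, change −5.
- Change-score bias: −5 − (−15) = +10 mmHg.
- SE of the difference = 50·√[2(1−r)]·√(2/n), from 18.7 (r = 0.3, n = 20) to 10.0 (r = 0.7, n = 30). The bias is thus 0.53 to 1.0 SE, and false positives are 8–17%.
- Baseline-adjusted: the treated baseline is 10 lower and follow-up levels are equal, so bias = 0 − r(−10) = 10r = +3 to +7 mmHg. False positives are about 5–11%.
- With a 1-day offset the biases are +5 (6–8%) and 5r = +1.5 to +3.5 (5–7%).
- If PF is rising instead, the signs reverse.

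**2. Regression to the mean.** If both groups follow one regression line and treated patients start D lower, the change score is falsely +(1−r)D. At D = 20 this is 6–14 mmHg, with 7–15% false positives. If the gap is stable instead, the change score is unbiased and the baseline-adjusted estimate is off by −(1−r)D (8–20% false positives). The documents cannot show which case holds.

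**3. PF day.** With no imbalance and no drug effect, the chance of at least one p < 0.05 is:
- one named day: 5%
- days 4 and 5: 7–9%
- days 4 and 14: 9–10%
- days 4, 5 and 14: 11–13%

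If day 3 is also counted as post-therapy, four candidate days give about 13–17% (correlation between days 0.7 down to 0.3).

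**4. CI wording.** Take a true effect of 40 mmHg, n = 20, r = 0.5 and no imbalance. The SD of change is 50·√[2(0.5)] = 50.
- One CI for the difference: SE = 50·√(2/20) = 15.8, and 40/15.8 = 2.53. Power is about 70%.
- Non-overlap of two 95% CIs: the means must differ by about 2 × 2.09 × 50/√20 = 46.8, more than the assumed effect. Power is about 35%. With equal SEs and no effect, this rule rejects in about 0.6% of trials by normal theory.

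**The case against.** The best defence is that much is implied. There is one ICU and one list of criteria, and the definition of the outcome by before and after a 3-day course rules out the early days. A change score deals with baseline level, and the plan does not claim randomised evidence. Part of this stands. The outcome wording does narrow the PF day, and the criteria may be meant for controls. Neither helps a control who has no therapy to date from, and a forward-looking exclusion judged from a chart needs a rule to keep later events out of the judgement.

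Several stronger readings are tempting but not supported:
- **Any of five follow-up values is open to choice (16–19% false positives).** Days 1 and 2 fall within treatment, so the outcome definition excludes them. The fair range for two or three post-therapy days is 7–13%, and it applies only if the best-looking day is reported. Nothing in the documents suggests such an intention.
- **Baseline adjustment is useless against a timing offset.** In the scenario above the later clock also lowers the treated baseline, so adjustment removes 30–70% of the bias. It reduces the problem without curing it.
- **Enrolment is the only time point given.** The plan also names the first 5 days, day 4 and day 14. The gap is that none is defined for controls.
- **The bias favours the drug.** Nothing says which group starts lower or is measured earlier in the illness.
- **The plan requires non-overlapping CIs.** The wording permits that reading but does not compel it. Under it, the false-positive rate falls and power is what is lost.

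**Conclusion.** The point holds and should be fixed before analysis. The only primary comparison rests on a change score, with no other adjustment, against a non-randomised group whose selection, Day 0 and PF day are not defined. No other section supplies them. Confidence is high in these omissions, which are plain in the text.

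The size is not known. The bias of up to 10 mmHg, the 5–17% false-positive rates in the timing scenarios and the 35% against 70% power all rest on an assumed SD, correlation, group size, PF course and effect. They show that ordinary imbalances could matter at this scale, not that they are present or in which direction. The same gap carries over to compliance and PEEP, which are to be analysed in a similar way.

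**What to change.** 1. **Controls and Day 0.** For treated patients, Day 0 is the day of first dose. Draw controls from consecutive standard-of-care patients in a stated calendar period who meet the same eligibility criteria as far as the chart allows, judged only on information available at Day 0. Match on days since intubation within a stated tolerance. The matched day is the control's Day 0, chosen without sight of later PF values.
2. **PF day.** Name one primary day after the 3-day course for both groups, for example day 4 after Day 0. That day lies within the first five whether they are numbered 0–4 or 1–5.
3. **Estimate.** Replace the comparison of CIs with one 95% CI for the between-group difference. Keep the plan's change score as the single primary estimate and pre-specify the baseline-PF-adjusted difference as the sensitivity analysis. If the two disagree, report the conclusion as dependent on the assumption about baseline differences.
4. **Reporting.** Tabulate baseline values and therapies received by group, and state conclusions as associations.
5. **Wording.** Reconcile the day-4 sampling sentence, which counts from randomisation, with the non-randomised design.

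**Cost.** This needs SAP wording and a chart-abstraction rule. PF, PEEP, ventilator data and therapies are already collected; intubation date is not listed explicitly and would have to be abstracted. Some controls will be lost to matching, and unmeasured confounding remains.

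### The primary PF comparison names no post-therapy day, does not adjust for baseline PF and leaves the daily values unused, so it is probably less precise than the collected data allow

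*Combined protocol and SAP*

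**What the plan says.** Research Design states: "Primary outcome measure will be change in arterial oxygen saturation to inhaled fraction of oxygen", taken from before to after treatment. The symbol given there is PaO₂/FiO₂, so I read this as the PF ratio. The Primary Statistical Plan and Analysis adds "Improvement in alveolar gas exchange will be defined as a change in PF ratio from baseline for both the treatment and control groups". The only rule it attaches for judging the two groups against each other is worded "with comparison of 95% CI between groups". Compliance and PEEP "will be analyzed in a similar fashion to change in PF ratio".

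Under Study Population and Data Collection, the plan takes, for the first "5 days and at day 14 if applicable, daily measurements of" PF, static compliance and PEEP. Treatment is given "twice daily for 3 days", and Research Design places the repeat blood and lavage sampling on day 4.

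The plan does not say:

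- which post-baseline day, or which summary over days, supplies the follow-up PF value;
- whether baseline PF enters as a covariate;
- whether the daily values are modelled together;
- whether the 95% CI is for the difference between groups or is two intervals set side by side.

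There is no sample size, SD or power for PF. The only power statement is a disclaimer: "The study is not powered to determine additional secondary endpoints such as mortality and length of hospitalization".

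**The concern.** If the analysis is one follow-up value minus one baseline value, the single baseline reading gets a fixed weight of −1 however noisy it is, and the other daily readings contribute nothing. When PF varies from day to day within a patient, both features widen the interval.

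The trial's main answer is a 95% CI for PF, from one center and with no stated sample size. Avoidable width makes an inconclusive result more likely. The unnamed follow-up day matters as well: with several post-baseline days available, the result depends on a choice that the plan leaves open.

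**Working it through.** The plan gives no figure to reproduce, so this compares interval widths in relative terms only. No absolute width can be given.

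**Inputs from the documents.** PF is measured daily for five days and treatment lasts three days, so days 4 and 5 fall after therapy.

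**Assumptions.** Day 1 is the first dosing day and supplies the baseline. The SD is the same each day (set to 1), data are complete and groups have equal baseline means. Between-day correlation r is either equal for all pairs of days (0.4 to 0.7) or autoregressive, AR(1), with day-to-day value r (0.6 to 0.9). Under AR(1) the correlations are r³ (days 1, 4), r⁴ (days 1, 5) and r (days 4, 5).

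**Variances per patient**

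- Reference, day 4 minus baseline: 2(1−r) under equal correlation; 2(1−r³) under AR(1).
- A, day 4 with baseline as covariate (no extra day used): 1−r²; 1−r⁶.
- B, mean of days 4 and 5 minus baseline (no covariate): 1+(1+r)/2−2r; 1+(1+r)/2−(r³+r⁴).
- C, mean of days 4 and 5 with baseline as covariate: (1+r)/2−r²; (1+r)/2−[(r³+r⁴)/2]².

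Example, equal r = 0.4: reference 1.20; C = 0.70−0.16 = 0.54; ratio 0.54/1.20 = 0.45.

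Example, AR(1) r = 0.9: reference 2(1−0.729) = 0.542; C = 0.95−(0.6926)² = 0.470; ratio 0.470/0.542 = 0.87.

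**Variance ratios to the reference**

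| Correlation | A: covariate only | B: averaging only | C: both | CI width, √C |
|---|---|---|---|---|
| Equal 0.4 | 0.70 | 0.75 | 0.45 | 0.67 |
| Equal 0.5 | 0.75 | 0.75 | 0.50 | 0.71 |
| Equal 0.6 | 0.80 | 0.75 | 0.55 | 0.74 |
| Equal 0.7 | 0.85 | 0.75 | 0.60 | 0.77 |
| AR(1) 0.6 | 0.61 | 0.93 | 0.49 | 0.70 |
| AR(1) 0.7 | 0.67 | 0.96 | 0.58 | 0.76 |
| AR(1) 0.8 | 0.76 | 1.00 | 0.70 | 0.84 |
| AR(1) 0.9 | 0.86 | 1.04 | 0.87 | 0.93 |

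Under C the CI is 7% to 33% narrower, which is worth 1/0.87 = 1.15 to 1/0.45 = 2.2 times as many patients.

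**Where the gain comes from.** The ratio C/A shows what the second day adds once baseline is in the model. Under equal correlation it is 0.45/0.70 = 0.64 to 0.60/0.85 = 0.71, a clear gain. Under AR(1) it is about 0.81 at r = 0.6, 0.93 at r = 0.8 and 1.00 at r = 0.9. There, baseline adjustment supplies most or all of the improvement.

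**Days 2 and 3.** With free group-by-day means and complete data, these days do not sharpen the day 4–5 contrast. The same holds for one fixed day: the model's variance for day 4 minus baseline at equal r = 0.6 is 0.80, identical to the two-value change score.

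**Baseline imbalance.** With equal-sized groups differing by d SDs at baseline, covariate adjustment inflates the variance by about 1+d²/4. That is 1.06 at d = 0.5 and 1.16 at d = 0.8. At AR(1) 0.9 the ratio becomes 0.87×1.06 = 0.92 and 0.87×1.16 = 1.01, so the gain is gone at about 0.8 SD. At equal 0.4 and d = 0.8 it is still 0.45×1.16 = 0.52.

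**The case against.** The strongest reply is that the plan never specifies a two-value change score. Change from baseline on each of the five days, with intervals, would also fit its wording. This stands: a reader might infer that the plan discards the daily values, but the documents show only that it does not say how they are used.

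A reader might also infer that daily collection by itself makes the planned interval too wide. It does not. Baseline adjustment needs only two values, days 2 and 3 add nothing with complete data, and averaging days 4 and 5 without the covariate gives variance ratios of 0.93 to 1.04 under AR(1).

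Next, precision is not the only criterion here. Research Design describes "A single center, non-randomized, controlled before-and-after clinical study was designed", for which comparing changes is a natural and valid analysis. When non-randomized groups start at different PF levels, a change score and a baseline-adjusted model can estimate different things, so replacing one by the other is partly a choice of estimand. This also stands, and it is why both results should be reported.

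A further reply is that averaging over days dilutes an effect that builds up during dosing. That is true of days 2 to 5. If the effect were 1/3, 2/3, 1, 1 over those days (an assumption), the mean would carry 75% of it, and the signal-to-SE ratio of an averaged change score would be only 0.95 to 0.97 of the two-value one despite the narrower CI. It does not count against days 4 and 5, which carry the full effect under that same pattern.

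**Conclusion.** The point holds in a limited form. The plan leaves the primary PF estimate undefined as to day, omits baseline adjustment and states no use for the daily values. On the natural reading it is less precise than the collected data permit. A baseline-adjusted mean over days 4 and 5 would narrow the CI by about 7% to 33%, given the assumed correlations, equal SDs, complete data and balanced baselines.

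The actual benefit is unknown, because the documents give no SD, correlation or sample size. It shrinks as the groups' baselines diverge, and the 7% is not a guaranteed minimum. Nothing here makes a change-score comparison invalid. This is a worthwhile improvement in definition and precision.

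**What to change.** In the Primary Statistical Plan and Analysis:

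1. Define the primary estimate as the between-group difference in PF averaged over days 4 and 5, with one 95% CI for that difference. State that day 1 is the first dosing day, which reading is the baseline, and which day counts as day 1 for controls, who have no dosing day.
2. Estimate it from a repeated-measures model on the post-baseline daily values with group, day, group-by-day, baseline PF as covariate and a within-patient correlation structure. Let the baseline slope differ by day, since the variances above use the slope specific to days 4 and 5.
3. Treat compliance and PEEP the same way, each with its own baseline.
4. Report the unadjusted change-score difference alongside, with its own CI, and show baseline PF by group so that readers can judge any disagreement.

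The cost is SAP wording and a somewhat more complex analysis, with no new data. The model is harder to explain than a simple difference, and the target becomes an average over two days rather than the value on one. A patient missing one of days 4 or 5 would still contribute, under a missing-at-random assumption; that possible benefit is not counted in the figures above.
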